4.6. Treatments

Table 4 presents how the dose groups will be presented on TFLs as treatment groups, including the order.

Table 4: Treatment Group Labels and Ordering

| Treatment Group Label | Order on TFLs |
|---------------------------|---------------|
| Placebo | 1 |
| 5 mg | 2 |
| 10 mg | 3 |
| 15 mg | 4 |
| All TERN-101 | 5 |
| Overall (where specified) | 6 |

Screen failures will be presented on by-patient listings where data is available.

4.7. Visits

4.7.1. Windows

Each visit will be denoted by its visit “Week”. The first dose day is denoted as Day 1. In data listings, the relative study day of all dates from first dose will be presented.

In the event of unscheduled visits or early treatment termination (ET) assessments, these will be reassigned to a scheduled visit for analysis purposes according to [Table 5](#) for on treatment assessments. If multiple assessments occur within a single visit window, after reassignment of unscheduled visits and ET assessments, the assessment closest to the target day of the visit window will be used in the analysis. If there is a tie, the later assessment will be used in the analysis.

Table 5: Treatment Period Visit Windows

| Target Scheduled Visit | Target Study Day ^a | Analysis Window Study Day ^a | |
|------------------------|-------------------------------|--|-----------------|
| | | Low | High |
| Baseline ^b | 1 | See Section 4.7.2 | |
| Week 2 | 15 | 2 | 22 |
| Week 4 | 29 | 23 | 36 |
| Week 6 | 43 | 37 | 50 |
| Week 8 | 57 | 51 | 71 |
| Week 12 ^c | 85 | 72 | 92 ^c |

^a Study day will be calculated from first dose of study drug.
^b Baseline is defined in [Section 4.7.2](#).
^c LFC and cTI by MRI will have no upper limit on Week 12.

The follow up visit (Week 16) will not be windowed. As described in [Section 8.7.1](#), sensitivity analyses will be conducted including only Week 16 assessments which are at least 22 days from last dose.

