1.3. Schedule of Activities (SoA)

Visit	Screening	Treatment Period ^d							Follow-Up ^b	ET ^a	Notes
		Week 0	Week 2	Week 4	Week 6	Week 8	Week 12	Week 16			
Study Day	-56 to Day -1	Day 1	15	29	43	57	85	113		Visit windows post randomization through Week 12: ± 3 days from the specified study day. Visit window Week 16: -1 week /+2 days from the specified study day.	
Procedures											
Written Informed Consent	X									Written informed consent may be obtained via telephone in accordance with Section 10.1.2. Screening may be initiated via telephone to avoid a visit to the site, if the patient is disqualified based on medical history.	
Patient Fasting	X	X	X	X	X	X	X	X	X	Patients must be in fasted state for at least 8 hours prior to blood collection and treatment administration where applicable.	
Randomization		X									
Review Inclusion and Exclusion Criteria	X	X								Recheck clinical status before randomization and first dose of study drug.	
Demographics	X									Includes age, sex, and race/ethnicity.	
Height and Weight	X	X	X	X	X	X	X	X	X	Height and weight are collected at Screening and will be used to calculate BMI for eligibility. Waist circumference is also measured at Screening. Only weight is collected Week 0, 4, 6, 8, 12, 16, and ET.	
Medical history	X									Includes details of illnesses and allergies, date(s) of onset, whether condition(s) is currently ongoing, and medication history, including alcohol use.	
Physical Examination	X	X	X	X	X	X	X	X	X	A complete physical examination will be performed at Screening and Week 16. A targeted physical examination will be performed at all other visits.	

	Screening	Treatment Period ^e							Follow-Up ^b	ET ^a	Notes
		Week 0	Week 2	Week 4	Week 6	Week 8	Week 12	Week 16			
Visit	Screening										
Study Day	-56 to Day -1	Day 1	15	29	43	57	85	113			Visit windows post randomization through Week 12: ± 3 days from the specified study day. Visit window Week 16: -1 week /+2 days from the specified study day.
Vital Signs	X	X	X	X	X	X	X	X	X	X	Includes temperature, pulse rate, respiratory rate, and blood pressure.
Chemistry ^c	X	X	X	X	X	X	X	X	X	X	Specific analytes are listed in Appendix 1. ALT/AST stability may be evaluated prior to randomization per Section 5. Increased monitoring criteria for elevated ALT and/or AST above 2 × Baseline or above 5 × ULN for < 1 week is outlined in Appendix 3.
Hematology ^c	X	X	X	X	X	X	X	X	X	X	Refer to Appendix 5 for the eGFR formula, to be calculated by central lab.

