7.3. Lost to Follow up

A patient will be considered lost to follow-up if he or she repeatedly fails to return for scheduled visits and is unable to be contacted by the study site.

[REDACTED]

- [REDACTED]
- [REDACTED]
- [REDACTED]

[REDACTED]

8. Study Assessments and Procedures

Study procedures and their timing are summarized in the Schedule of Activities. Protocol waivers or exemptions are not allowed.

Adherence to the study design requirements, including those specified in the Schedule of Activities, is essential and required for study conduct.

All screening evaluations must be completed and reviewed to confirm that potential patients meet all eligibility criteria. The investigator will maintain a screening log to record details of all patients screened and to confirm eligibility or record reasons for screening failure, as applicable.

The maximum amount of blood collected from each patient over the duration of the study is not expected to exceed 550 mL. Repeat or unscheduled samples may be taken for safety reasons or for technical issues with the samples.

If a patient requires home quarantine due to SARS-CoV-2 infection or exposure, or due to COVID-19 symptoms or other associated concern with attending an in-person study visit, in accordance with [Section 6.8.1](#), home health care visits may be made available to continue study assessments in the patient's home where feasible, and/or remote visits via telephone, telemedicine, or other appropriate virtual communication may be substituted for a visit to the site.

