8.1.7. Clinical Laboratory Assessments

See [Appendix 1](#) for the list of clinical laboratory tests to be performed and to the Schedule of Activities for the timing and frequency.

The investigator must review the laboratory report, document this review, and record any AEs per the guidance in [Appendix 6](#). The laboratory reports must be filed with the source documents.

Shifts of clinically significant Grade 3 or Grade 4 laboratory abnormalities or any clinically significant laboratory abnormalities considered possibly related to study drug in the opinion of the investigator should be repeated within 48-72 hours and followed to resolution or until stable.

All protocol-required laboratory assessments, as defined in [Appendix 1](#), must be conducted in accordance with the laboratory manual and the Schedule of Activities.

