8.6. Multiple Comparisons/Multiplicity

There will be no adjustment for multiplicity. Statistical testing will be considered nominal, descriptive, and exploratory.

8.7. Secondary Efficacy Analyses: Percent Change from Baseline in ALT Levels at Week 12

Descriptive statistics of ALT values, change from baseline, and percent change from baseline values will be presented by treatment group for each visit using the Efficacy Analysis Set. In addition, figures of mean (\pm SD) ALT values, change from baseline, and percent change from baseline will be presented over time by treatment group.

Analyses of percent change (and separately change) from baseline will be carried out using an ANCOVA model at Week 12 with percent change (and separately change) from baseline as the dependent variable including treatment group as a fixed effect and baseline as a covariate. The primary analysis of percent change (and separately change) in ALT at Week 12 will be carried out using available observed data only, without imputation for missing data.

The estimates of least-square (LS) means, standard errors (SE), and 90% and 95% CIs will be presented by treatment group. Estimates of the LS mean difference between pooled TERN-101 (All TERN-101) and placebo, and each pairwise comparison between placebo and each active dose of TERN-101, will be presented with the associated standard error of the difference, and 90% and 95% CIs of the difference.

The same ANCOVA model will be used to analyze the last on-treatment value for Week 12, to be labelled as “End of Treatment”. For patients who complete Week 12, the Week 12 value will be used. For patients who do not complete treatment, the last value on treatment will be used.

The same ANCOVA model will be presented for each post-baseline visit using observed data only.

The distribution of percent change values will be evaluated visually for normality assumptions. If normality assumptions are violated, i.e. data are not normally distributed, a Wilcoxon Rank Sum Test will be used to compare each TERN-101 dose to placebo, and pooled TERN-101 (All TERN-101) to placebo. The median differences and 90% and 95% CIs of the median differences between treatment groups will be constructed using Hodges-Lehmann estimate.

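### The visit-window rule gives the scheduled sample no priority, so after an early visit a result-triggered repeat can displace a high ALT or AST value in the efficacy models

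*SAP*

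**What the plan says.** **Selection rule (SAP 4.7.1).** Unscheduled and early-termination assessments are reassigned to scheduled visits using Table 5, with a qualifier limiting this to assessments on treatment. When a window then holds several values, "the assessment closest to the target day of the visit window will be used in the analysis". On ties: "If there is a tie, the later assessment will be used in the analysis". The Week 12 window runs from Day 72 to Day 92 around target Day 85.

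**Visit timing (Protocol 1.3).** "Visit windows post randomization through Week 12: ± 3 days from the specified study day".

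**What produces repeats.** Under Protocol 8.1.7, clinically significant Grade 3 or 4 shifts, and clinically significant abnormalities thought possibly related to study drug, "should be repeated within 48-72 hours and followed to resolution or until stable". The schedule of activities separately refers to "Increased monitoring criteria for elevated ALT and/or AST above 2 × Baseline or above 5 × ULN", adds a duration of under one week, and sends the reader to Appendix 3, which is redacted. The opening of Protocol Section 8 adds: "Repeat or unscheduled samples may be taken for safety reasons or for technical issues with the samples". Appendix 1 also lets the investigator order extra tests.

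**Where the selected value is used.** SAP 8.7 fits an ANCOVA to Week 12 ALT on observed data, and "The same ANCOVA model will be presented for each post-baseline visit using observed data only". Section 8.8.2 applies the same model to AST and GGT. Section 4.7.3 accepts a scheduled or a windowed Week 12 value as End of Treatment. None of the visible text restricts these analyses to scheduled samples. At baseline, by contrast, Section 4.7.2 averages all pre-dose values, so no repeat displaces anything.

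**The concern.** When a repeat is ordered because the first result was high, the pair is not exchangeable. The first value was selected for being high, and the second will often be lower through regression to the mean or because a transient rise is resolving. A rule that can keep only the second removes high values and has no matching route for removing low ones, since a low ALT does not trigger a repeat.

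Regression to the mean alone acts similarly in every arm and largely cancels in the comparison. Transient elevations that are more frequent in one arm do not cancel. ALT at Week 12 is the only secondary efficacy endpoint, and the drug's effect on transaminases is of interest in both directions, so the by-visit estimates should not depend on whether a visit happened to be a day or two early.

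**Working it through.** The documents give no figure to reproduce: the sample size was not set by power and the power table is redacted.

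**1. When does a repeat win?** Let the scheduled visit fall s days from target (s = −3 to +3) and the repeat g days later. The repeat is used if |s + g| ≤ |s|, the equality coming from the tie rule. For a visit k days early (s = −k) this is g ≤ 2k. For a visit on or after target it never holds.

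| Days early (k) | 48 h repeat (g = 2) | 72 h repeat (g = 3) | 7-day repeat |
|---|---|---|---|
| 3 | replaces | replaces | no |
| 2 | replaces | replaces | no |
| 1 | replaces (tie) | no | no |
| 0 or late | no | no | no |

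**2. Share of repeats that replace.**
- Visit days uniform over seven days: 3/7 at 48 h and 2/7 at 72 h. With half the repeats at each, (3/7 + 2/7)/2 = 5/14 = 36%.
- Clustered, for example 40% on target and 15%, 10% and 5% at 1, 2 and 3 days either side: 0.05 + 0.10 + 0.15/2 = 22.5%.
- Tightly clustered, for example 66% on target and 10%, 5% and 2% either side: 0.02 + 0.05 + 0.10/2 = 12%.

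These count g from the scheduled sample. If the 48–72 hours run from receipt of the result, g is longer and the share smaller.

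**3. Bias in one arm's mean percent change.**
Bias = −(share of arm with a repeat) × (share replaced) × (mean fall from scheduled to repeat value, in points).

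Assume 10% of the arm has a triggered repeat, and three possible falls:
- 50 points;
- 92 points: a 2.5-fold rise half resolved on the log scale, 2.5^0.5 = 1.58, so +150% becomes +58%;
- 107 points: a threefold rise with 60% remaining on the log scale, 3^0.6 = 1.93, so +200% becomes +93%.

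| Fall | Uniform (5/14) | 22.5% | 12% |
|---|---|---|---|
| 50 | −1.8 | −1.1 | −0.6 |
| 92 | −3.3 | −2.1 | −1.1 |
| 107 | −3.8 | −2.4 | −1.3 |

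Simulations of 2,000,000 patients per scenario, varying within-patient variation and the trigger, agree. Between-arm bias was about −2.0 to −3.3 points for 10% with half-resolving 2.5-fold rises (22.5% to uniform), and within-arm bias was −4.2 for 10% with the threefold case under uniform days.

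**4. Other courses of the elevation (same 2.5-fold simulation, 10% affected).**
- Persisting at the repeat: between-arm bias −0.65 to +0.04.
- Still rising (2.5^1.2 = 3.0, so +150% becomes +200%): +0.5 to +1.8.

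**5. Scale.** Ten percent of 24 is 2.4 patients, of whom 2.4 × 5/14 = 0.9 would be replaced under uniform days, so in practice the effect is none or one or two patients. One patient moved from +150% to +60% shifts a 24-patient mean by 90/24 = 3.8 points. The standard error of a pairwise difference is SD × √(2/24): 7.2, 8.7 or 11.5 points for an assumed SD of 25, 30 or 40. An arm containing such elevations would have a larger SD.

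The simulations attach 48–72 hour timing to a multiple-of-baseline trigger. The visible text gives that timing only to the Protocol 8.1.7 repeats.

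**The case against.** **Week 12 may be exempt.** Reassignment is limited to on-treatment assessments, and the protocol makes Week 12 the last day of treatment. A repeat two or three days later would then be off treatment and not reassigned. This is a fair reading, but the term is not defined in the visible text, Table 5 runs to Day 92, and Section 4.7.3 accepts a windowed Week 12 value. The Week 12 application is therefore ambiguous. Earlier visits are exposed either way.

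**Not all repeats follow high values.** A reader might infer that repeats are ordered only after elevations. The protocol contradicts this: technical and discretionary samples also enter. The supportable statement is that the visible triggers specific to ALT and AST point upward. No visible trigger is specific to GGT, which would be redrawn mostly alongside ALT and AST, so selection on GGT is weaker.

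**The direction is not guaranteed.** Correct. A material downward shift needs elevations that partly resolve by the repeat. Nothing in the documents says how often that will happen, and Protocol 2.2.3 reports no transaminase elevation above 1.5 times the upper limit of normal in two of the healthy-subject studies.

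**The rule is prespecified, identical across arms, and testing is nominal.** True, and the rank-based fallback in SAP 8.7 would blunt single outliers. But a rule applied identically still biases a comparison when its trigger depends on the outcome and the arms differ in how often it fires.

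**Conclusion.** The defect is real but conditional. SAP 4.7.1 can discard a high scheduled ALT or AST value in favour of its repeat, in 36% of 48–72 hour repeats if visit days are uniform and about 12–22% if they cluster. With 10% of an arm affected and partly resolving elevations, the mean is lowered by about 2 to 4 points under uniform days and 0.6 to 2.4 under clustering. That is below one standard error of a pairwise difference. The share affected, the fall, the visit-day distribution and the SD are all assumptions.

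The by-visit ALT and AST models are affected. So are the Week 12 and End of Treatment ALT analyses, unless the on-treatment qualifier excludes samples after the last dose.

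A reader might go further and conclude that the rule systematically favours the drug or conceals liver signals. The documents do not support that. Bias vanishes or reverses if elevations persist or rise, and the peak stays in the safety output through worst post-baseline shifts (SAP 9.3.4), treatment-emergent grade increases (9.3.1), Table 9 and the listings. Appendix 3 of the protocol and parts of SAP 8.7.1 are redacted, so an exception there cannot be excluded.

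**What to change.** Replace the selection sentence in SAP 4.7.1 with:

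> *For efficacy and by-visit change analyses, the valid scheduled-visit value is used. An unscheduled or ET value is used only if the window has no valid scheduled value (missing or technically compromised), choosing the one closest to the target day.*

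The validity clause matters: without it, a compromised scheduled sample would beat its valid repeat. Validity should be judged from laboratory flags, not from the size of the result.

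Also define on treatment for this section, state whether samples after the last dose can be assigned to Week 12, and keep the present closest-to-target rule as a sensitivity analysis.

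With this wording a repeat can no longer displace a valid scheduled value, so this bias is zero by construction. The cost is a few lines of SAP text and one sort key in the analysis dataset, and no patient is lost. The downside is that a scheduled value slightly further from the target day will sometimes be used. Because the SAP is already final, the change can be documented in the clinical study report, as SAP Section 1 allows.

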4.7.2. Definition of Baselines

The baseline value for statistical analyses of quantitative laboratory parameters is defined as the mean of all available evaluations, including any unscheduled or repeat assessments, prior to the first administration of study drug, unless otherwise specified. If there is only one evaluation prior to the first administration of study drug, then the available data from this evaluation will be used as the baseline value.

For glucose and lipid parameters, only assessments taken while fasting for 8 hours will be included in the baseline derivation.

The baseline value for analyses of qualitative parameters (e.g., normal/abnormal) is defined as the last evaluation prior to the first administration of study drug.

The baseline value for analyses of weight, body mass index (BMI), and electrocardiogram parameters is defined as the last evaluation prior to the first administration of study drug.

4.7.3. Definition of End of Treatment

The End of Treatment value will be defined as the Week 12 value, either scheduled or windowed per Table 5. If a Week 12 value is not available, the last non-missing on or before the last dose date will be used.

5. ANALYSIS SETS

Table 6 defines the analysis sets to be used.

Table 6: Analysis Sets

| Analysis Sets | Description |
|----------------------|--|
| Screened | All patients who sign the informed consent form (ICF). |
| Randomized | All patients who are randomized into any one of treatment groups. Treatment assignment will be based on the randomized treatment. |
| [REDACTED] | [REDACTED] |
| Pharmacodynamic (PD) | All randomized patients who received at least 1 dose of study drug (TERN-101 or placebo) and for whom at least one post-baseline assessment of FGF19, 7αC4, [REDACTED] is available. Treatment assignment will be based on the treatment actually received. The PD analysis set will include patients with trough concentrations and with intensive PD sampling as part of the PK/PD substudy. |
| Safety | All patients who received at least 1 dose of study drug. Treatment assignment will be based on the treatment actually received. |
| Efficacy | All randomized patients who received at least 1 dose of study drug. Treatment assignment will be based on the randomized treatment. |
| Per Protocol (PP) | All randomized patients who have completed the study without any protocol deviations affecting the interpretation of the efficacy, PK, or PD results. Treatment assignment will be based on the treatment actually received. |

| Analysis Sets | Description |
|---------------------|--|
| Treatment Completer | 
All patients who complete 12 weeks of treatment with at least 80% compliance based on study drug accountability.
 
Treatment assignment will be based on the randomized treatment.
 |

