Of the 96 patients randomized, 24 patients will take part in an intensive PK and pharmacodynamic (PD) collection after the first dose and after the last dose of study drug. This includes 6 patients at each TERN-101 dose level, and 6 patients in the placebo group. Patients who are not participating in the PK/PD sub-study will have trough PK/PD sampling only.

The total duration of study participation will be approximately 24 weeks, consisting of an 8-week Screening Period, a 12-week Treatment Period and a 4-week Follow-up Period.

Disclosure Statement:

This is a parallel-group treatment study.

Number of Patients:

Approximately 96 patients will be randomly assigned to treatment with TERN-101 tablet or matching placebo.

Patients who are randomized but do not receive study drug for any reason may be replaced.

Study Centers Planned:

Approximately 40 centers in the United States.

Intervention Groups and Duration:

The total study duration will be approximately 24 weeks, consisting of an 8-week Screening Period, a 12-week Treatment Period and a 4-week Follow-up Period.

Screening Period

The 8-week Screening Period initiates upon signing an Informed Consent, at which point eligibility criteria will be reviewed. Each eligible patient will be scheduled for Week 0/Day 1.

Treatment Period

The 12-week double-blind, randomized Treatment Period will initiate at Week 0/Day 1 after confirming eligibility. The blinded study drug (TERN-101 tablet or placebo) will be orally administered once daily in the morning, without regard to food.

Patients will return to the site at Weeks 2, 4, 6, 8, and 12 for safety and laboratory assessments. Study drug will be dispensed at Week 0/Day 1, Week 4, and Week 8. Week 12 is the last day of treatment.

Intensive PK/PD sampling will be performed in 24 patients participating in the PK/PD sub-study after the first dose (Week 0/Day 1) and after the last dose of study drug (Week 12).

[figure not shown]
Imaging (MRI-PDFF) will be completed at Week 0, Week 6, and Week 12. An MRI is performed at early termination (ET) only if not done within the prior 4 weeks, and the patient has had at least 4 weeks of dosing.

Follow-up Period

All patients will return to site for follow up safety assessments at Week 16.

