9.3. Analysis Sets

The following analysis sets are defined:

Analysis Sets	Description
Enrolled	All patients who sign the ICF
Randomized	All patients who meet all eligibility criteria and are randomized into any one of treatment groups.
[REDACTED]	[REDACTED]
Pharmacodynamic (PD)	All randomized patients who received at least 1 dose of study drug (TERN-101 or placebo) and for whom PD markers can be evaluated.
Safety	All randomized patients who received at least 1 dose of study drug and have post dose safety data. Patients will be analyzed according to the intervention they actually received.
Efficacy (Full analysis Set [FAS])	All randomized patients who received at least 1 dose of study drug. Patients will be analyzed according to the intervention they are planned to receive.
[REDACTED]	[REDACTED]

A patient is considered to have completed the study if he/she has completed all phases of the study including the last scheduled assessment in the Follow-Up Period.

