2.3.2. Secondary Endpoints

- Percent change from baseline in ALT levels at Week 12
- Plasma PK for TERN-101 and its main metabolite TRN-000971

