8.8.3. NASH and Fibrosis Biomarkers

Markers of hepatic fibrosis and apoptosis include CK-18 (M30 and M65), PIIINP, TIMP-1, HA, and Pro-C3. Descriptive statistics of biomarker values, change from baseline, and percent change from baseline will be presented by treatment group for each visit using the Efficacy Analysis Set.

Change (and separately percent change) from baseline will be analyzed using the same ANCOVA model presented in [Section 8.7](#). Sensitivity analyses using the PP and Treatment Completer Analysis Sets will be presented if the analysis set differs from the Efficacy Analysis Set by more than 10 patients total.

Assessments of normality will be performed as described in [Section 8.7](#).

[REDACTED]

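### The Per Protocol set requires attendance at the Week 16 off-drug visit, so missing that visit alone removes patients with full Week 12 data from the biomarker sensitivity analyses

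*SAP*

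**What the plan says.** SAP Section 5, Table 6, defines the PP set as "All randomized patients who have completed the study without any protocol deviations affecting the interpretation of the efficacy, PK, or PD results". The visible SAP text does not say what completing the study means. Protocol 9.3 does: the patient must have "completed all phases of the study including the last scheduled assessment in the Follow-Up Period". The protocol synopsis fixes the two dates that matter: "Week 12 is the last day of treatment", and "All patients will return to site for follow up safety assessments at Week 16". SAP Section 11, which lists changes from the protocol's planned analyses, records no change to the meaning of study completion.

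Table 6 also defines a Treatment Completer set: "All patients who complete 12 weeks of treatment with at least 80% compliance based on study drug accountability". It has no Week 16 condition.

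PP is visibly used in two places. SAP 7.2 gives baseline tables for PP and Treatment Completer, and SAP 8.8.3 gives sensitivity analyses of the NASH and fibrosis biomarkers in the same two sets. Both uses are conditional. In 8.8.3 the results "will be presented if the analysis set differs from the Efficacy Analysis Set by more than 10 patients total".

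**The concern.** A per-protocol set should keep patients who were treated and measured as planned for the results in question. Here the entry condition extends past those results. The biomarkers are sampled at Weeks 0, 6 and 12 (and at early termination), yet a patient must also attend a safety visit four weeks after dosing ended in order to count. A missed Week 16 visit cannot make a Week 12 Pro-C3 value less valid, but under the definition it removes that value from the PP analysis.

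Two things follow. Week 6 and Week 12 results in PP are conditioned on an event that happens later. And patients removed for this reason count toward the difference that decides whether PP results are shown, so a PP table could appear, and could differ from the Efficacy table, for reasons unrelated to adherence or relevant deviations.

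**Working it through.** The documents state no figure to reproduce on this point. The check is a comparison of definitions, followed by illustrative arithmetic.

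**Definitions side by side**

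1. PP requires study completion (SAP Table 6).
2. Study completion requires the last Follow-Up assessment (protocol 9.3).
3. That assessment is Week 16, Day 113. Treatment ends at Week 12, Day 85 (Schedule of Activities). The gap is 113 − 85 = 28 days off drug. The stated periods agree: 8 + 12 + 4 = 24 weeks, with treatment ending at Week 12 and follow-up at Week 16.
4. So a patient with complete Week 12 data and no Week 16 visit is not a study completer and is not in PP.
5. The SAP itself separates the two kinds of completion. Section 7.1 counts early treatment discontinuation and early study discontinuation separately, and Table 6 has a set built on treatment completion. Reading the PP wording as treatment completion would therefore be a departure from the text.

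**What PP is used for, and when it is measured**

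| Output under SAP 8.8.3 | Week 16 value planned? | Source |
|---|---|---|
| CK-18, PIIINP, TIMP-1, HA, Pro-C3 | No | Protocol 1.3 |
| ELF score | No | SAP 8.8.3.2 |
| FIB-4 score | Yes | SAP 8.8.3.1 |
| NAFLD fibrosis score | Yes | SAP 8.8.3.3 |

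**Size**

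Inputs: 96 patients, 24 per arm (protocol 4.1; 4 × 24 = 96). The display rule needs more than 10 patients to differ, so at least 11, and 11/96 = 11.5%. One patient is 1/24 = 4.2% of an arm.

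Let d be the share of patients who miss Week 16 only. The documents give no value, so d is assumed over a range. It is applied to all 96, which treats every randomized patient as a treatment completer, so the counts are an upper case for each d.

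- Patients removed = 96 × d
- PP per arm = 24 × (1 − d), with equal loss across arms
- Standard error inflation = √(1/(1 − d))
- Chance that Week 16 loss alone meets the display rule = P(X ≥ 11), X ~ Binomial(96, d)

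| d (assumed) | Removed | PP per arm | SE inflation | P(X ≥ 11) |
|---|---|---|---|---|
| 5% | 4.8 | 22.8 | 2.6% | 0.009 |
| 10% | 9.6 | 21.6 | 5.4% | 0.364 |
| 15% | 14.4 | 20.4 | 8.5% | 0.870 |

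The loss of precision is small throughout. The display rule is the more sensitive part: at 5% it would almost never be met by Week 16 loss alone, and at 15% it usually would be.

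**The case against.** The strongest reply is that little depends on this.

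- **A neighbouring set already helps.** Treatment Completer stands beside PP wherever PP is visibly used, under the same display rule, and has no Week 16 condition. A compliant patient who misses only Week 16 stays in that set. This stands in part. Treatment Completer does not screen for protocol deviations and assigns patients by randomized rather than received treatment, so it does not replace PP.
- **Some outputs do use Week 16.** FIB-4 and the NAFLD fibrosis score follow the 8.8.3 approach and are calculated at Week 16. Liver function tests are also analysed at follow-up (SAP 8.8.2). Requiring the full schedule is a known per-protocol convention. This stands for those Week 16 outputs, but it gives no reason to apply the condition to biomarkers that have no Week 16 sample.
- **Being shown is not a loss.** If the rule is met, readers see an extra table, and SAP 7.1 plans a by-patient listing of reasons for exclusion from each set. This also stands. What remains is that the table could differ from the Efficacy result for reasons unrelated to adherence.

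Three stronger readings are tempting and are not supported. A reader might infer that Week 12 ALT, MRI or PD results are affected. No visible text applies PP to them: the main ALT analysis uses observed Week 12 data in the Efficacy set (SAP 8.7), and PD changes use the PD set (SAP 8.10.3). Parts of the SAP are blacked out, so other uses of PP are possible but cannot be shown. A reader might also infer that every PP output precedes Week 16, which the two scores above contradict. Finally, a reader might infer a demonstrated bias. Attendance at Week 16 could depend on tolerability or response, but nothing in the documents shows that it does, and the visit window and the COVID-related home or remote visits would limit missed visits.

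**Conclusion.** The point holds in a limited form. Read together, SAP Table 6 and protocol 9.3 remove patients with complete Week 12 data from PP for missing a later off-drug visit. For CK-18, PIIINP, TIMP-1, HA, Pro-C3 and ELF, that condition has no bearing on the validity of the result.

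The number affected is unknown, and the 5% to 15% range is an assumption. Within it, the cost in precision is under 10%, while the chance of triggering display through Week 16 loss alone runs from negligible to likely. The primary safety analysis, in the Safety set, and the main Week 12 ALT analysis are unaffected, and all efficacy testing is declared nominal and exploratory (SAP 8.6). This is a cheap improvement to a supplementary analysis, of low severity.

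**What to change.** In SAP Table 6, define PP as randomized patients who completed the 12-week treatment period and the Week 12 assessments, with no protocol deviation that affects interpretation of the efficacy, PK or PD results. For outputs that use Week 16, such as FIB-4 and the NAFLD fibrosis score at that visit, use the PP patients with an observed Week 16 value. As a minimum, state in the SAP what completing the study means for PP.

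The cost is one line in Table 6 and a matching change to the programming of the set. There are two small downsides: the PP count will no longer match study completers in the disposition table, and PP will overlap more with Treatment Completer. The two sets will still differ in their deviation and compliance conditions.
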